3.3. Safety Endpoints

Most of the safety outcomes are defined by the Sponsor's standards. These outcomes include

- Incidence and severity of adverse events (AEs), serious adverse events (SAEs), and withdrawals due to adverse events.
- Clinical laboratory values (chemistry, hematology parameters).
- Vital signs (blood pressure, pulse rate and temperature measurements),ECG-based parameters.
- Incidences of severe and opportunistic infection AEs; herpes virus infection AEs; clinically significant categorical increases in hepatic enzymes Aspartate aminotransferase (AST), and Alanine aminotransferase (ALT) and total bilirubin, and potential cases meeting Hy's Law criteria for increased risk of drug-induced liver injury (DILI); major adverse cardiovascular events (MACE), including pulmonary embolism (PE) and deep vein thrombosis (DVT), Cerebrovascular accident (CVA); Adverse events (AEs) for decreased renal function, acute kidney injury, clinically significant increases in serum creatinine (Scr) and decreases in estimated glomerular filtration rate (eGFR).

The additions include the parameters of the audiology test.

An adverse event (AE) is considered a Treatment-Emergent Adverse Event (TEAE) if the event started during the effective duration of treatment. All events that start on or after the first dosing day for B7921023 will be flagged as TEAEs. The algorithm will not consider any events that started prior to the first dose date. If an AE starts on the same day as the first dose date, it will be considered treatment emergent unless the CRF data indicates otherwise via explicitly recording time for AE onset which was occurred before the first treatment dosing.

3.4. ~~CCI~~ PD Endpoints

The ~~CC~~/PD endpoints include:

~~C~~
~~C~~
~~I~~

- Concentrations of anti-citrullinated protein antibodies (ACPA), rheumatoid factor (RF) and IP-10;

- CCI

4. ANALYSIS SETS

For purposes of analysis, the following analysis sets are defined.

Table 7. Analysis Sets

Data Set	Description
Modified Intent to Treat (mITT)	All participants randomly assigned to investigational product who take at least 1 dose of investigational product. Participants will be analysed according to the randomized intervention.
Sensitivity Set (SNS)	All participants randomly assigned to investigational product who take at least 1 dose of investigational product. It is a subset of mITT data set where the observations that may be affected by the poor compliance or use of concomitant medications are excluded. Participants will be analysed according to the randomized intervention.
Safety Set	All participants randomly assigned to investigational product who take at least 1 dose of investigational product. Participants will be analysed according to the intervention they actually received.

CCI

PD Data Set (PD)	All participants randomly assigned to investigational product and who take at least 1 dose of investigational product and have at least 1 of PD parameters of interest.
------------------	---

Appendix 1 shows how to assign observations to the discrete set of study visits based on the observation time. CCI

5. GENERAL METHODOLOGY AND CONVENTIONS

Final analyses will occur after database lock after Last Participant Last Visit (LPLV).

5.1. Hypotheses and Decision Rules

The primary clinical hypothesis is that mean decrease at week 12 in DAS28-CRP score in one or both combo arms CCI exceeds the mean decrease in the reference (tofacitinib) treatment arm. The null hypothesis is that the mean decrease in DAS28-CRP score at week 12 is identical in the control (Tofacitinib arm) and combination arms. There are no multiplicity adjustments planned for this study.

5.2. Analyses of Continuous Data

The estimands E1 and E1* are described in the [Section 2.1](#). The analysis for the estimand E1 is based on the mITT data set while the analysis for the estimand E1* is based on the sensitivity data set. We denote the analyses of interest by the names of the corresponding estimands and use the name D1 for the descriptive analysis. The analyses names, data sets and analyses methods are listed in the Table 8.

Table 8. Analyses of Continuous Data

Analysis Name	Data Set	Analytic Approach
E1	mITT	MMRM
E1*	Sensitivity data set (SNS)	MMRM
D1	mITT	Descriptive statistics

For the E1 and E1* analyses we will use the MMRM (Mixed Model for Repeated Measures) estimator while the usual descriptive estimator will be used for estimating E1*. The MMRM analysis will use the change from baseline value of the continuous variable as an outcome and treatment, scheduled study visit, baseline value of the variable of interest, treatment by visit interaction and baseline by visit interaction as fixed effects. The model will use the unstructured covariance matrix. The MMRM model is described in multiple textbooks including the books by Fitzmaurice, Laird and Ware (2011)⁴ and by Mallinckrodt and Lipkovich (2017).³ **CCl**

The p-values and 90% confidence intervals will be reported for the E1 analysis of primary and secondary efficacy outcomes for the comparisons of combination arms with tofacitinib arm. Only the confidence intervals with 90% coverage will be used for all other analyses of continuous outcomes.

5.3. Analyses of Binary Data

The estimands E2, E2*, and E3 are described in the [Section 2.1](#). The analyses for the estimands E2, E3, are based on the mITT data set while the analysis for the estimand E2* is based on the sensitivity data set. We denote the analyses of interest by the names of the corresponding estimands and denote the analyses based on descriptive statistics by D2, D3. The analyses names, data sets and analyses methods are listed in the Table 9.

Table 9. Analyses of Binary Data

Analysis Name	Data Set	Analytic Approach
E2	mITT	BSC + CZ (ratio of probabilities) + NRI
E2*	Sensitivity data set (SNS)	BSC + CZ (ratio of probabilities) + NRI
E3	mITT	BSC + CZ (difference of probabilities) + NRI
D2	mITT	BSC + CZ (ratio of probabilities) + NOIMP
D3	mITT	BSC + CZ (difference of probabilities) + NOIMP

*BSC+CZ= Blyth-Still-Casella + Chan and Zhang, NRI- non-responder imputation, NOIMP-no imputation.

We will use the Blyth-Still-Casella (Blyth and Still (1983)⁵ and Casella (1986)⁶) method for the estimation of the probability of response at a given visit and a given treatment arm and Chan and Zhang (Chan and Zhang, 1999)⁷ method for comparison of the probability of response across the treatment arms. For the E2, E2* and E3 analyses we will use the non-responder imputation treating missing value of the binary outcome as non-response with the exception of the two special cases of the reason for missing data. These special reasons for missing data include missingness related to the COVID infection (either patient illness or COVID-related problem of attending the visit) and missingness when subject attended the visit but some of the components for the calculation of the outcome (eg, ACR20) are missing. The observations that are missing for these special reasons will be excluded from the calculation of the probabilities of response at a given visit.

The p-values and 90% confidence intervals will be reported for the E2 and E3 analysis of key secondary and secondary efficacy outcomes for the comparisons of combination arms with tofacitinib arm. Only the confidence intervals with 90% coverage will be used for all other analyses of binary outcomes.

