2.1. Study Objectives, Endpoints and Estimands

A definition of an estimand includes four components (ICH, 2019, Mallinckrodt et al, 2020).^{1,2}

1. The population targeted by the scientific question.
2. The endpoint (variable) to be obtained for each patient.
3. The population-level summary for the variable that provides a basis for a comparison between treatment conditions and metric for a comparison between the treatment groups.
4. How to account for the intercurrent events (ICEs). The intercurrent events are defined as the post-randomization events that alter the course of the randomized treatment.

We will use 5 different estimands presented in the [Table 2](#). These estimands are characterized by the different definition of the key features above. We will use the estimand from the group E1-E3 corresponding to a particular study objective as the main estimand and the estimands E1*, E2* as supportive. The goal of the estimands E1* and E2* is to confirm a qualitative similarity of the results of primary and key secondary analyses based on the different approaches to the adjustment of the analyses for the presence of the intercurrent events.

The estimands E1-E3 rely on the “treatment policy” approach to the efficacy comparison across the treatment groups. The approach compares treatment efficacy across the treatment groups irrespective of the participant's compliance with study treatment and use of concomitant medications. No intercurrent events are included into the definition of these estimands and therefore no accounting for the intercurrent events is required. The estimands E1*, E2* classify the events of poor compliance to the randomized treatment or use of concomitant medications as the intercurrent events and use “hypothetical” strategy for accounting for these events. This strategy aims at the mitigation of the confounding of the comparison of the efficacy of randomized treatment by the intercurrent events. The estimands E1* and E2* will be used for the support of the primary and key secondary objective of the study.

We will also report the additional supportive analyses of continuous and binary outcomes based on the cross-sectional, visit specific summaries. These summaries are based on the data observed at a particular visit (also baseline observations for change from baseline). The analyses may be viewed as an estimation of the treatment effect in the population of subjects who stay in the study up to a given study visit.

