In our presentation we will use labels E1, E1*, E2, E2*, E3 for the analyses which have as their target the estimands presented in the Table 2 and labels D1, D2, D3 for the descriptive analyses.

The qualitative similarity of the results of these different analyses is expected to support the conclusion based on the results of primary and key secondary analyses.

Table 2. Characterization of the Estimands

Notation for the Estimand	Population targeted by the Scientific Question	Type of Endpoint	Population-level Summary for a given Treatment	Metric for a Comparison between the Treatment Groups	Account for the ICE
E1	All treated study participants	Continuous	Mean change from baseline	Difference of mean values	None
E2	All treated study participants	Binary	Mean probability of response	Ratio of probabilities of response.	None
E3	All treated study participants	Binary	Probability of response	Difference of probabilities of response	None
E1*	All treated study participants	Continuous	Mean change from baseline	Difference of mean values	Censoring of observations (visits within a subject) potentially affected by the ICE
E2*	All treated study participants	Binary	Mean probability of response	Ratio of probabilities of response.	Censoring of observations (visits within a subject) potentially affected by the ICE

The correspondence between the study objectives, endpoints and estimands is shown in [Table 3](#).

[figure not shown]
Table 3. List of Study Objectives, Endpoints and Estimands

Objectives	Endpoints	Key Estimand [Supportive estimand]
Primary	Primary	Primary

 To compare the efficacy of each of 2 treatment combination arms to tofacitinib alone at Week 12 	
 Change from baseline DAS28-CRP at week 12. 	E1 [E1*]
Key Secondary	Key Secondary	Key Secondary

 To compare the remission rates for each of 2 treatment combinations arms to tofacitinib alone at Week 24 	
 DAS28-CRP remission at Week 24. 	E2 [E2*]
Secondary	Secondary	Secondary

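### E2* is declared a hypothetical-strategy estimand, but SAP 5.3 analyses it with non-responder imputation, which makes it wholly or partly a composite one

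*SAP*

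**What the plan says.** - **Strategy.** SAP 2.1 treats poor compliance and concomitant medication use as intercurrent events (ICEs) for E1* and E2* and assigns both a hypothetical strategy. Its purpose: "This strategy aims at the mitigation of the confounding of the comparison of the efficacy of randomized treatment by the intercurrent events". Table 2 gives the handling as "Censoring of observations (visits within a subject) potentially affected by the ICE".
- **Data set.** E2* is analysed on the sensitivity set (SNS), which SAP 4 describes as a "subset of mITT data set where the observations that may be affected by the poor compliance or use of concomitant medications are excluded".
- **Estimator.** SAP Table 9 gives E2* the same exact methods and the same non-responder imputation (NRI) as E2. The text of 5.3 reads: "For the E2, E2* and E3 analyses we will use the non-responder imputation treating missing value of the binary outcome as non-response". It names two exceptions, COVID-related missingness and an attended visit with missing components, and adds: "The observations that are missing for these special reasons will be excluded from the calculation of the probabilities of response at a given visit".
- **Sister estimand.** SAP 5.2 and Table 8 analyse E1* on the SNS with MMRM.
- **Reporting.** E2* falls under the 5.3 sentence "Only the confidence intervals with 90% coverage will be used for all other analyses of binary outcomes". Table 9 also plans a descriptive analysis D2 on the mITT set, "BSC + CZ (ratio of probabilities) + NOIMP".
- **Intended use.** SAP 2.1 says of the full group of analyses: "The qualitative similarity of the results of these different analyses is expected to support the conclusion".

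**The concern.** A hypothetical strategy asks how often participants would have been in remission at Week 24 had the ICE not occurred. Scoring an ICE case as a failure answers another question: how often participants were in remission *and* had no ICE. That is a composite strategy. SAP 2.1 declares the first, and the rule in 5.3, as it stands, delivers the second in whole or in part.

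What is at stake is interpretation. SAP 2.1 uses E2* to show that the key secondary result is robust to a different treatment of ICEs. A participant who left before Week 24 is a failure in E2 through NRI. If the same participant is a failure in E2*, part of the agreement between the two follows from the scoring rule. E2* is then a weaker check than 2.1 claims, and a composite result could be reported under a hypothetical label.

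**Working it through.** **1. Inputs.** Protocol 9.2.2 assumes 26% remission on tofacitinib and a ratio of 1.7, and 26% × 1.7 = 44.2% as stated. Its power of about 84% reproduces at 100 per arm (83.5% with a Wald test on the log ratio, 85.8% with a pooled normal test). That figure belongs to E2 and is not in dispute. No power is computed for E2*, which has no test criterion. Neither document gives an ICE or censoring rate, so every rate below is an assumption.

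**2. Who is affected.** Protocol 6.4 and 7.2 withdraw participants who interrupt treatment for more than 7 consecutive days, or who are below 80% compliance for 2 consecutive visit periods. Protocol 8.11 discontinues those with a flare needing prohibited medication and those needing extra pain medication for RA symptoms for more than 5 consecutive days. After a 4-week follow-up these participants leave the study, so many would have no Week 24 value. A smaller group can have an ICE and still attend Week 24: a single low-compliance period does not trigger withdrawal, and 8.11 allows a prohibited medication to be stopped and the participant monitored.

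**3. Two readings of SAP 4 and 5.3.**

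| | Attended Week 24 after an ICE | Left after an ICE, Week 24 missing |
|---|---|---|
| A: a removed visit is a missing value | failure, even if remission was observed | failure |
| B: a removed visit leaves the denominator | excluded | failure, through ordinary NRI |
| E1* (MMRM) | left missing | left missing |

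Reading A is the direct one, because 5.3 names E2* under NRI and states denominator exclusion only for its two special reasons. Reading B removes part of the mismatch but not all of it.

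**4. Effect on the ratio.** Let p be an arm's remission rate without ICEs, c the share of Week 24 values lost to the ICE rule, and r the remission rate those participants would have had.

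- NRI rate = p − c·r
- Exclusion rate = (p − c·r)/(1 − c)
- NRI ratio ÷ exclusion ratio = (1 − c_comb)/(1 − c_tofa), whatever r is

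| Assumed censoring, tofacitinib/combination | Factor |
|---|---|
| equal | 1.00 |
| 12%/10% | 0.90/0.88 = 1.02 |
| 15%/10% | 0.90/0.85 = 1.06 |
| 20%/10% | 0.90/0.80 = 1.125 |
| 10%/20% | 0.80/0.90 = 0.89 |

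**5. Effect on the arm rates.** Assume 15% ICEs per arm, unrelated to response, half of them gone by Week 24, and no other missing data.

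| Analysis | Multiplier | Tofacitinib | Combination |
|---|---|---|---|
| E2 | 0.925 | 24.1% | 40.9% |
| E2*, reading A | 0.85 | 22.1% | 37.6% |
| E2*, reading B | 0.85/0.925 = 0.919 | 23.9% | 40.6% |
| E2*, all ICE cases excluded | 1 | 26.0% | 44.2% |

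The ratio is 1.70 in every row because censoring is balanced. Reading B stays close to E2, since both score the leavers as failures.

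**6. Is exclusion always right?** No. Take 26% true remission in both arms and 20%/10% censoring. If the censored would remit at 26%, NRI gives 23.4/20.8 = 1.125 and exclusion gives 1.00. If none of them would remit, NRI gives 26/26 = 1.00 and exclusion gives (26/0.90)/(26/0.80) = 0.89. The true ratio is 1.00 in both cases.

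**The case against.** The strongest reply is that the construction of the sensitivity set cannot be fully seen. Redactions follow the analysis sets in SAP 4 and the visit windows in Appendix 1, and the contents list a Table 14 on inputs for binary outcomes whose body is not shown. No sentence says that a visit removed from the SNS is a missing value for NRI; SAP 4 and 6.7 speak of exclusion and removal. The NRI text in 5.3 may concern only visits that were truly missed. The public text also does not say whether one earlier low-compliance period makes a Week 24 visit potentially affected.

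Much of this stands. A reader might infer that the plan certainly scores observed remissions as failures; the text supports that as the direct reading, not as a certainty. A reader might also infer that programmers would produce different results from this text. That is not shown, because they hold the unredacted SAP. Nor should one picture many observed remissions being discarded: the withdrawal rules leave a narrow group.

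What does not stand is that the exclusion reading cures the problem. Under it, participants who left after an ICE are still failures through ordinary NRI, so label and estimator disagree on any reading of the public text.

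**Conclusion.** The point holds. On the public text E2* is wholly composite (reading A) or partly composite (reading B), although 2.1 and Table 2 call it hypothetical. D2 is free of NRI but does not censor ICEs, so it does not fill the gap.

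The consequence is limited. A reader might infer that the key secondary conclusion or the type I error is at risk. The documents do not support that: E2* is supportive and has no p-value, and E2, E3 and alpha are unaffected. A reader might also infer that the E2* ratio is biased. That needs censoring to differ between arms, whereas the SAP's version history expects balance and 6.7 will report removals by arm and visit. The shifts of 1.06 and 1.125 rest on assumed imbalances, and neither NRI nor exclusion is right under every assumption about the censored. The defect is one of labelling and of how much reassurance agreement with E2 can give.

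**What to change.** In SAP 5.3 and Table 9, do one of the following:

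1. Exempt from NRI, for E2* only, both the ICE-censored visits and the Week 24 values missing because the participant left after an ICE. Name the estimator and its assumption. Exclusion from the denominator keeps exact inference and needs no new method, but assumes that censoring is unrelated to response. Multiple imputation of Week 24 DAS28-CRP under missing at random is an alternative; it adds a programme and gives up exact inference for this one analysis.
2. Keep NRI and relabel E2* as composite in 2.1 and Table 2.

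If redacted text already defines how SNS-removed visits are handled, a cross-reference from 5.3 will do, with the label aligned to that rule. Leave E2 and E3 as they are, and read E2* beside D2 and the removal proportions planned in 6.7. The cost is one or two sentences, or a change of label.

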5.4. Analysis of Safety Data

Safety data will be summarized based on observed-case data by treatment arm.

6. ANALYSES AND SUMMARIES

6.1. Efficacy Analyses

The tables below summarize analyses of continuous and binary efficacy endpoints.

Table 10. Analyses of Continuous Efficacy Endpoints

N	Observations	Group	E1	D1	E1*
1	DAS28-CRP at week 12		X	X	X
2	TJC28,	ClinRo	X	X	
3	TJC68	ClinRo	X	X	
4	SJC 28	ClinRo	X	X	
5	SJC 68	ClinRo	X	X	
6	PhGA	ClinRo	X	X	

CCI

15	DAS28-CRP	COMP-CONTI	X	X	
----	-----------	------------	---	---	--

CCI

The analysis #1 for primary outcome will include data collected up to and including week 12 and will report the summaries for week 12 visit. All other analyses will include all collected data and will report summaries at all study visits.

Table 11. Analyses of Binary Efficacy Endpoints

N	Observations	Group	E2	D2	E2*	E3	D3
1	DAS28-CRP remission rate at week 24		X	X	X		
2	ACR 20	ACR				X	X
3	ACR 50	ACR				X	X
4	ACR 70	ACR				X	X
5	ACR 90	ACR				X	X

CCI

6.2. Baseline and Other Summaries and Analyses

6.2.1. Baseline Summaries

Demographics and baseline characteristics will be summarized for each arm and total according to Pfizer standards.

6.2.2. Study Conduct and Participant Disposition

Participant's evaluation, disposition, discontinuation will be summarized according to Pfizer standards.

6.2.3. Study Intervention Compliance

A participant will be considered compliant with the dosing regimen if they receive at least 80% of the expected number of doses in accordance with the protocol. The number and percentage of participants who are compliant with the dosing regimen, number of dosing days and number of applications, and amount of intervention used will be summarized.

6.2.4. Concomitant Medications and Nondrug Treatments

Prior drug and non-drug treatment, concomitant drug and non-drug treatment will be summarized according to Pfizer standards.

6.3. Safety Summaries and Analyses

All safety analyses will be performed on the safety analysis set population ([Section 4](#)).

The safety data will be summarized in accordance with Pfizer Data Standards. All safety data will be summarized descriptively through appropriate data tabulations, descriptive statistics, categorical summaries, and graphical presentations.

6.3.1. Adverse Events

Overall standard AE endpoints for this study are:

- Incidence of TEAEs;
- Incidence of SAEs;
- Incidence of AEs leading to discontinuation;
- Incidence of special interest AEs: severe and opportunistic infection, herpes virus infection, MACE including PE and DVT, CVA, and decreased renal function, and acute kidney injury.

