4. STUDY DESIGN

4.1. Overall Design

This is a Phase 2, 24-week, multicenter, randomized, double-blind, 5-arm, parallel group, active comparator study to evaluate the efficacy and safety profiles of 2 combinations of investigational products (IPs): PF-06650833 coadministered with PF-06651600 (PF-06650833 + PF-06651600) and PF-06650833 coadministered with tofacitinib (PF-06650833 + tofacitinib), as well as the efficacy and safety of each IP individually in the absence of background MTX in participants with moderately - severely active RA who have had an inadequate response to MTX (MTX-IR).

The primary objective is to demonstrate superiority of at least 1 combination arm to tofacitinib monotherapy with the primary endpoint being change from baseline (CFB) in DAS28-CRP at Week 12. A key secondary endpoint is remission rates of the combination and individual IPs at Week 24, as defined by DAS28-CRP <2.6. The study is powered to show statistical superiority of the combination to tofacitinib monotherapy at Week 12.

[figure not shown]
Up to approximately 450 participants are planned to be randomized globally into the study to ensure at least up to approximately 370 participants complete at least 12 weeks of active dosing (assuming a dropout rate of approximately 18%). Participants will be randomly assigned to 1 of the following 5 treatment groups in a 4:4 3:3:4 ratio: PF-06650833 + tofacitinib, PF-06650833 + PF-06651600, PF-06650833, PF-06651600, and tofacitinib (see also study schematic design in [Section 1.2](#)).

After an up to 28-day screening period, eligible participants will enter a 24-week active treatment period after being randomly assigned to one of the 5 treatment groups shown in [Section 1.2](#). Participants will be in this study for a total of approximately 32 weeks which includes the screening period, the 24-week active treatment period, and a 4-week drug-free follow-up period.

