Serious infections defined as any infection (viral, bacterial, or fungal) requiring parenteral antimicrobial therapy or hospitalization for treatment or meeting other criteria that require the infection to be classified as a serious adverse event.	Treatment with all study drugs will be discontinued and the participant withdrawn from this study. Participant followed until resolution or deemed medically stable by PI.
Opportunistic infection judged significant by investigator.	Treatment with all study drugs will be discontinued and the participant withdrawn from this study. Participant followed until resolution or deemed medically stable by PI.
Other	
Participants who have a flare of RA requiring treatment with prohibited concomitant medication are to be discontinued from the study treatment.	Treatment with all study drugs will be discontinued and participants will be treated for their RA according to local standard of care (SoC) practice. Upon discontinuation of the study treatment, participants will enter a FU period of 4 weeks, after which they will complete the FU/EOS visit and will be withdrawn from the study.

Condition	Action
Participants who require additional/increased doses of pain control medication for more than 5 consecutive days for treatment of increased RA symptoms should be discontinued from the study treatment.	Treatment with all study drugs will be discontinued and participants will be treated for their RA according to local standard of care (SoC) practice. Upon discontinuation of the study treatment, participants will enter a FU period of 4 weeks, after which they will complete the FU/EOS visit and will be withdrawn from the study.
Participants who at any time from Week 12 to Week 24 do not manifest a minimal clinical response as defined by meeting ACR20 criteria.	Treatment with all study drugs will be discontinued and participants will be treated for their RA according to local standard of care (SoC) practice. Upon discontinuation of the study treatment, participants will enter a FU period of 4 weeks, after which they will complete the FU/EOS visit and will be withdrawn from the study.

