9.4.2. Safety Analyses

All safety analyses will be performed on the safety population derived from all participants enrolled.

Endpoint	Statistical Analysis Methods
Primary	
The safety data will be summarized in accordance with Pfizer Data Standards. All participants who receive at least 1 dose of IP (safety population) will be included in the safety analyses. All safety data will be summarized descriptively through appropriate data tabulations, descriptive statistics, categorical summaries, and graphical presentations. Safety endpoints for the study include:
 
 • Treatment-emergent AEs and SAEs; • Withdrawals from active treatment due to AEs; • Serious infections, defined as any infection (viral, bacterial, and fungal) requiring hospitalization or parenteral antimicrobials; • Safety laboratory tests (eg, hematology [including coagulation panel], chemistry and lipid profiles); • Vital signs; • ECG. 
Change from baseline on laboratory data, vital signs and ECG will be additionally summarized. Participant listings will also be produced for these safety endpoints.

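### The visible SAP text summarises adverse events only as incidences, while the ACR20 stopping rule ties observation time to efficacy, so at equal hazards crude incidence tilts modestly upward in the more effective arm

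*SAP*

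**What the plan says.** - **AE summary.** SAP 6.3.1 names four AE endpoints, each an incidence: treatment-emergent AEs ("Incidence of TEAEs"), serious AEs, AEs leading to discontinuation, and AEs of special interest. SAP 6.3 adds that "The safety data will be summarized in accordance with Pfizer Data Standards". Protocol 9.4.2 is equally general: "All safety data will be summarized descriptively through appropriate data tabulations, descriptive statistics, categorical summaries, and graphical presentations".
- **Stopping rule.** Protocol 8.11 applies to "Participants who at any time from Week 12 to Week 24 do not manifest a minimal clinical response as defined by meeting ACR20 criteria". All study drugs are stopped, local standard-of-care RA treatment begins, and "participants will enter a FU period of 4 weeks, after which they will complete the FU/EOS visit and will be withdrawn from the study".
- **Full course.** Protocol 4.1 describes a "24-week active treatment period, and a 4-week drug-free follow-up period", which is 28 weeks after randomization for a completer.
- **AE collection.** Protocol 8.3.1 runs active collection to at least 28 calendar days after the last dose.
- **Treatment-emergent flag.** SAP 3.3 first limits treatment-emergent events to those starting within an effective treatment duration, which it does not define. It then says: "All events that start on or after the first dosing day for B7921023 will be flagged as TEAEs".
- **Exposure.** SAP 6.2.3 summarises dosing days under compliance and SAP 6.2.2 summarises discontinuations. Neither is linked to the AE tables.

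**The concern.** A participant who stops at Week 12 for lack of ACR20 response is watched for AEs for about 16 weeks; a participant who responds throughout is watched for about 28. The share of each type in an arm is decided by how well the arm works. The trial is built to find that the combinations work better than tofacitinib, so if it succeeds the arms will differ in observation time because of efficacy.

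A proportion with at least one event rises with time observed. Comparing such proportions between arms therefore mixes the event rate with the length of observation. This matters because Protocol 2.1 sets a dual aim: more efficacy with an acceptable safety profile. The tilt runs against whichever arm is more effective. It is largest against a weak monotherapy, which is the contrast needed to judge whether combining drugs adds harm.

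**Working it through.** **Plan's own figure.** The documents state no AE incidence, ACR20 rate or expected exposure by arm, so there is nothing to reproduce on this point. The size rests on the assumptions below.

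**Inputs from the documents.** Stop from Week 12 and 4 weeks of follow-up (Protocol 8.11); 24 + 4 weeks for a completer (Protocol 4.1); AE collection to 28 days after last dose (Protocol 8.3.1); about 100 participants per combination and tofacitinib arm and 75 per other monotherapy arm (Protocol 9.2.1).

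**Assumptions.** ACR20 response r = 75% (combination), 60% (tofacitinib), 45% (a weaker monotherapy); the same constant weekly hazard h in every arm; 28-week risk P of 5%, 20% or 50%; at first, every non-responder stops at Week 12 and every responder completes. The 75% versus 60% contrast is not arbitrary. Protocol 9.2.1 plans a DAS28-CRP difference of 0.5 with SD 1.20, a standardized effect of 0.5/1.2 = 0.417. On a latent normal scale this moves 60% to Φ(0.253 + 0.417) = 74.9%. The 45% is only an illustration.

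**Step 1: time.**
- Mean treatment = 12 + 12r: 21.0, 19.2 and 17.4 weeks.
- Mean AE observation = 16 + 12r: 25.0, 23.2 and 21.4 weeks.

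**Step 2: crude incidence at equal hazards.** h = −ln(1 − P)/28; crude incidence = r·P + (1 − r)·(1 − exp(−16h)). For P = 20%, h = 0.00797 and the 16-week risk is 11.97%. The combination arm gives 0.75 × 20 + 0.25 × 11.97 = 17.99%; tofacitinib gives 0.60 × 20 + 0.40 × 11.97 = 16.79%. SE of a difference = √[p₁(1 − p₁)/n₁ + p₀(1 − p₀)/n₀].

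| 28-week risk | 75% arm | 60% arm | 45% arm | Ratio vs 60% | Difference (SE), points | Ratio vs 45% | Difference (SE), points |
|---|---|---|---|---|---|---|---|
| 5% | 4.47% | 4.16% | 3.84% | 1.08 | 0.3 (2.9) | 1.17 | 0.6 (3.0) |
| 20% | 17.99% | 16.79% | 15.58% | 1.07 | 1.2 (5.4) | 1.16 | 2.4 (5.7) |
| 50% | 45.68% | 43.08% | 40.49% | 1.06 | 2.6 (7.0) | 1.13 | 5.2 (7.6) |

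The tilt is 0.11 to 0.37 SE versus tofacitinib and 0.2 to 0.7 SE versus the 45% arm.

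**Step 3: sensitivity.**
- *Only half of non-responders stop at Week 12 and the rest complete.* The completing share becomes 87.5%, 80% and 72.5%. At P = 20% the incidences are 19.00%, 18.39% and 17.79%, ratios 1.03 and 1.07. Over the three risks the ratios are about 1.03 versus tofacitinib and 1.06 to 1.07 versus the 45% arm.
- *Equal response rates.* The ratio is 1.00.
- *Tofacitinib ACR20 from 50% to 70%, combination shifted by 0.417, 28-week risk 2% to 80%, all non-responders stopping.* The ratio is 1.03 to 1.09 and the difference 0.1 to 3.2 points. The more effective arm would show the higher crude incidence in about 52% to 69% of trials instead of 50%.
- *Events clustered early (hazard falling to one third after Week 4), 75% versus 60%.* The ratio is 1.04 to 1.06.

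**Step 4: do the alternatives remove it?**
- *Incidence through Week 12* = 1 − exp(−12h), the same in every arm: 2.17%, 9.12% and 25.7% for the three risks. Equality here does not need a constant hazard.
- *First events per 100 participant-years* under a constant hazard = 5200h in every arm, for example 5200 × 0.001832 = 9.53 for the 5% event. If the hazard falls to one third after Week 4, the rate ratio is 0.98 versus tofacitinib and 0.96 versus the 45% arm; if to one fifth, 0.97 and 0.94. This bias is smaller than that of crude incidence, but it favours the longer-observed arm.

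**The case against.** **Size.** A reader might infer that a more effective combination will look less safe. The documents and the arithmetic do not support that. Versus tofacitinib the tilt is well under half a standard error, safety is descriptive, and no visible decision rule turns on the AE contrast. Full stopping at Week 12 is also an upper-end case. The rule acts at any time from Week 12 to Week 24, and investigators are blinded to post-randomization hsCRP (Protocol 8.1.1.5), a possible ACR component. All of this stands.

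**Sponsor standards.** A reader might infer that exposure-adjusted rates will never be produced. SAP 6.3 defers to standards that are not in the documents, so neither their presence nor their absence there can be shown. What can be said is that the visible text names only incidences. An exposure imbalance created by this trial's own stopping rule should be dealt with in this trial's SAP.

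**Treatment-emergent window.** A reader might infer that the flag has no end. SAP 3.3 does refer to an effective treatment duration, and AE collection has a planned horizon. The fair criticism is that this duration is undefined and fits poorly with the sentence that follows it. Events after standard-of-care RA drugs start in non-responders would add to the less effective arms, so they could partly offset the tilt.

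**Target of estimation.** Cumulative incidence under the assigned strategy, including its stopping rule, is a legitimate quantity, and Protocol Section 3 defines no estimand for safety. That is a reason to keep crude incidence, not to leave it as the only named summary.

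**Partial handling.** Dosing days and discontinuations are tabulated, so a reader can see that exposure differs, but not what this does to AE comparisons.

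**Conclusion.** The point holds as a modest, systematic tilt. AE observation time depends on efficacy by design, the visible SAP text names only incidences, and at equal hazards the more effective arm has the higher expected crude incidence. Under the assumed 75%/60%/45% response rates, the ratio is about 1.03 to 1.08 versus tofacitinib and about 1.06 to 1.17 versus the 45% arm, as half to all non-responders stop at Week 12. It vanishes if response rates are equal. The ranges assume a constant hazard and no other dropout. Early-clustered events, disease-related AEs in less effective arms and standard-of-care events could shrink or offset the tilt. It is not a certain or large false signal, and it does not show that the sponsor's standards lack exposure adjustment. The change is worth making because the imbalance is foreseeable and the remedy is cheap.

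**What to change.** In SAP 6.3.1, keep crude incidence and add for each AE category:

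1. **Incidence through Week 12**, before the ACR20 stop acts, as the main like-for-like comparison. Note that it misses later events, and that stops for worsening RA at the investigator's discretion can occur earlier (Protocol 4.1).
2. **First-event rate per 100 participant-years**, counting time from first dose to the event, or to the earlier of last dose + 28 days and start of standard-of-care RA treatment. State that it is neutral only under a roughly constant hazard and can slightly favour the longer-exposed arm if events cluster early.

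In SAP 3.3, state the end of the treatment-emergent window, so that the effective treatment duration and the sentence flagging all events from first dose agree.

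The protocol also differs on whether non-responders are discontinued from the study (Sections 1.2 and 6.5.1) or from study treatment (Sections 1.1, 4.1 and 8.11). These passages must be reconciled, because they fix the AE observation window. The stopping rule itself is not in question here.

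Cost: a few extra safety tables. AE, dosing and concomitant-medication dates are already collected, so no new data are needed.
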